- 1) Survey questionnaires: Questionnaires pose no more than minimal risk to the participants. There is a potential for perception of privacy intrusion. However, the subjects have the right to refuse to answer any of the questions or stop at any time, and there is no penalty for refusing to participate. No complications have been recorded. The proposed questionnaires are validated, widely used, and were received well by the participants.
- 2) ¹¹C ER 176 PET/CT scan: PET scans and the tracers used are generally safe. In a recent study, no adverse or clinically detectable pharmacologic effects were observed with ¹¹C-ER176 for any of the 17 subjects
- 3) EUS-guided core biopsy: Mild self-limiting serosal bruising and/or localized hematoma formation at the sites of EUS biopsies. Other standard risks of an upper endoscopy include pain (abdominal and throat), aspiration and extremely rarely, death. Serious risk of bleeding and frank perforation is rare (<1 in 1000).

3. Potential Benefits of the Proposed Research to the Subjects and Others

The proposed research has the potential to remarkably enhance our understanding of visualizing immune dysregulation in the gastric muscle of patients with diabetic gastroparesis. This will have a downstream effect of identifying immune dysfunction in other GI conditions. Broadly, this can revolutionize assessment of inflammatory milieu in areas that are not easily or safely amenable for a biopsy. As of now, there likely will not be a direct benefit to the gastroparesis patients as we still do not have clear therapies to target immune dysfunction in gastroparesis. Given the anticipated mechanistic insights to the participants in this research proposal, and to others with diabetic gut dysfunction, the benefits outweigh the risks.

4. Importance of the Knowledge to be Gained

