The proposed research has the potential to develop a new approach to diagnose immune dysregulation in diabetic gastroparesis, a disorder with unmet clinical need. Specifically, this project is aiming to determine if a special radio ligand ¹¹C ER 176 based PET/CT imaging can detect activated macrophages in the gastric muscle of patients with diabetic gastroparesis. Additionally, these results will be validated using actual assessment of gastric muscle tissue to determine cellular markers that associate with pro- or anti-inflammatory macrophages. This study will open a novel paradigm for assessment of immune dysregulation in the GI tract which will have utility for a broad range of GI conditions. This pilot and feasibility proposal will generate novel preliminary evidence for future investigations in this area and treatment trials. The risks to the participants are fairly low with questionnaires, PET/CT scan and EUS with biopsies which are safe procedures. Given the repertoire of the PI and study team in conducting mechanistic, endoscopic and imaging studies of this nature as well as the precautions taken to minimize discomfort or adverse effects, the overall risk of this study is fairly low. There is a high likelihood (e.g., investigator team's record and expertise, validated methods) of obtaining meaningful, useful information for the proposed aim.

5. Data and Safety Plan

Subject Safety: Adverse Events

Adverse Event Grading

Attribution scale: An adverse event is defined as either an expected side effect that is of a serious nature, or an unexpected side effect regardless of severity. All events will be graded as to their attribution (unrelated to protocol: possibly, probably, or definitely related to protocol). Any event that is reported to either the PI or his designated research associates by the subject or medical staff caring for the subject and which meets the criteria will be documented as such.

Expected risks: These risks will be addressed in the protocol and consent form. The expected risks include:

- Loss of confidentiality through unauthorized release of private medical information. This is unlikely since all data are collected in electronic form and access is protected by user identification ID.
- Questionnaires pose some risk of causing emotional distress but these are validated and widely used questionnaires which are typically well received.

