- ¹¹C ER 176 based PET/CT imaging is generally safe and no adverse effects were noted in published studies. However, there is radiation exposure which can be harmful. Additionally, there could be intolerance to the IV injection of radio ligand.
- EUS with core gastric biopsies are generally low risk, especially with an advanced endoscopist like [name] who will perform this procedure on all proposed participants. Adverse effects include abdominal pain, bleeding, and perforation. Rarely, these adverse events can lead to sepsis and death. However, the probability of a serious adverse event is 1 in 2000 or less, making the procedure quite safe.

Plan for Reporting both Anticipated and Unanticipated Adverse Events.

Any adverse event that is reported generates a report, which will be submitted to the Mayo Clinic IRB. The report will include a description of the event, when and how it was reported, as well as any official chart records or documentation to corroborate the event or the reporting of the event. All adverse events will be graded as mild, moderate, or severe. Any severe and/or unanticipated adverse event will be reported within 24 hours to the IRB. All other adverse events will be reported in a timely fashion to the IRB, preferably within 2 weeks. All adverse events will be summarized annually and submitted to the IRB.

Subject Safety: Safety review plan and monitoring

Safety Reviews: The PI will review the safety and progress of this study on a quarterly basis.

Annual Review: The PI will review this protocol on a continuing basis for participant safety and include results of the review in the annual progress reports submitted to the IRB. The annual report will address: (1) whether adverse event rates are consistent with pre-study assumptions; (2) reason for dropouts from the study; (3) whether all participants met entry criteria; (4) whether continuation of the study is justified on the basis that additional data are needed to accomplish the stated aims of the study; and (5) conditions whereby the study might be terminated prematurely.

Data Integrity

Adherence Statement: The DSMP outlined will adhere to the protocol approved by the Mayo Clinic IRB (IRB-C which handles research conducted in the Mayo Clinic CCaTS).

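### The adverse event definition leaves out expected non-serious events and conflicts with the reporting plan in the same section

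*Combined protocol and SAP*

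**What the plan says.** Under Adverse Event Grading, section F.5 defines the term: "An adverse event is defined as either an expected side effect that is of a serious nature, or an unexpected side effect regardless of severity". The same paragraph then says that an event reported to the investigator or the research staff "which meets the criteria will be documented as such".

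Other parts of the document bear on how this works:

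- **F.1.c Potential risks and F.2.b Specific risks and precautions** name the minor harms of the biopsy. F.2.b lists "Mild self-limiting serosal bruising and/or localized hematoma formation at the sites of EUS biopsies" and adds: "Other standard risks of an upper endoscopy include pain (abdominal and throat), aspiration and extremely rarely, death". It puts serious bleeding and frank perforation at under 1 in 1000.
- **F.5 Expected risks** mentions possible intolerance to the tracer injection. For the biopsy it says "Adverse effects include abdominal pain, bleeding, and perforation", with no condition that these be serious, and that "the probability of a serious adverse event is 1 in 2000 or less". It does not name bruising or hematoma.
- **F.5 reporting plan** is headed as covering anticipated as well as unanticipated events and says "All adverse events will be graded as mild, moderate, or severe". Severe and/or unanticipated events go to the IRB within 24 hours, and all others preferably within 2 weeks.
- **F.5 Annual Review** asks "whether adverse event rates are consistent with pre-study assumptions".
- **Section D** plans 12 participants (4 with diabetic gastroparesis, 4 with diabetes only, 4 healthy). Only the gastroparesis patients have endoscopy and biopsy. All participants are watched for adverse events during the injection.

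**The concern.** The definition has two limbs: expected and serious, or unexpected. An expected event that is not serious satisfies neither. The harms most likely after a full-thickness needle biopsy of the stomach wall are the ones the protocol predicts and calls mild, so the definition removes the events most likely to occur.

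The study is a pilot meant to inform larger investigations and treatment trials. A successor study would want to know how often patients had pain or a hematoma after the biopsy, and whether the injection was tolerated. If staff apply the definition as worded, the adverse event record cannot answer that, and a zero could be read as good tolerability. If they follow the reporting plan instead, the same events are counted. The result would then depend on which paragraph of F.5 a coordinator relies on.

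**Working it through.** The plan states no event count or safety calculation to reproduce. The check is mainly a comparison of texts, followed by simple binomial arithmetic.

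**Step 1. Classify events under each rule in F.5.**

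| Event | Adverse Event Grading definition | Reporting plan, read on its own terms |
|---|---|---|
| Expected, not serious | Not an adverse event | Anticipated; graded; IRB preferably within 2 weeks, or 24 hours if graded severe |
| Expected, serious | Adverse event | IRB within 24 hours if graded severe, otherwise preferably within 2 weeks |
| Unexpected, any severity | Adverse event | Unanticipated; IRB within 24 hours |

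The rules differ in the first row. If the reporting plan inherits the definition, its 2-week stream can hold only events that are expected, serious and yet not graded severe. That is a very small class for a stream meant to take everything else. If it does not inherit the definition, the two paragraphs contradict each other.

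**Step 2. Follow one mild hematoma through the text.**

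- Expectedness judged by F.1.c and F.2.b: expected and not serious, so not documented as an adverse event.
- Expectedness judged by the F.5 list, which names bleeding but neither bruising nor hematoma: it can be classed as unexpected, hence an adverse event at any severity and reportable within 24 hours.
- Reporting plan read on its own terms: an anticipated mild event, reported preferably within 2 weeks.

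The same finding has three possible fates.

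**Step 3. Size of the lost count.** Input: n = 4 biopsied patients (section D). The documents give no rate p for minor biopsy events, so p is an assumed range. Expected number of patients with an event = 4p; P(at least one) = 1 − (1 − p)^4.

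| Assumed p | 4p | P(at least one) | Count under the literal definition |
|---|---|---|---|
| 5% | 0.2 | 1 − 0.95^4 = 18.5% | 0 |
| 10% | 0.4 | 1 − 0.90^4 = 34.4% | 0 |
| 25% | 1.0 | 1 − 0.75^4 = 68.4% | 0 |
| 50% | 2.0 | 1 − 0.50^4 = 93.8% | 0 |

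**Step 4. What the annual review can still do.** The rates stated for the biopsy concern serious events, which the definition captures.

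- At 1 in 2000: 1 − 0.9995^4 = 0.20% chance of any serious event in 4 patients.
- At 1 in 1000: 1 − 0.999^4 = 0.40%.
- After 0 events in 4, the one-sided 95% upper limit is 1 − 0.05^(1/4) = 52.7%.

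The comparison can be made, although 4 patients barely test either figure. That weakness comes from the sample size, not from the definition. For expected non-serious events the review has neither a count nor a stated rate.

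**The case against.** The strongest reply is that F.5 as a whole does not mean to exclude minor events. Its list of expected risks treats abdominal pain and bleeding as adverse effects with no test of seriousness, and its reporting plan grades events from mild upward and covers anticipated ones. The definition says only which events are documented as adverse events. It does not say that others go unrecorded, and the investigator's quarterly review of safety and progress is not expressly limited to defined adverse events. Nor is safety an endpoint: the stated aim is the feasibility of the imaging, and the primary endpoint is tracer biodistribution.

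Much of this stands. It shows an internal conflict rather than a clear, total exclusion, and it limits the consequence, since no endpoint or planned analysis changes. It does not remove the problem. The definition is the only place that says what counts, and the later text either inherits it or contradicts it.

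A reader might infer three stronger things that the documents do not support:

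- **That bruising, hematoma and pain could never be counted.** Serious cases meet the definition on any reading, and bruising or hematoma could be counted as unexpected because the F.5 list omits them.
- **That the annual rate review cannot work.** It can be run for serious and unexpected events, and the stated biopsy rates are for serious events.
- **That the two risk figures contradict each other.** One bounds serious bleeding and perforation, the other any serious adverse event. If the second holds, the first holds too.

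**Conclusion.** The point holds as a faulty stated rule in conflict with its own section. Taken literally, the definition gives a count of zero for expected non-serious events whatever their true rate. It affects minor biopsy harms in 4 patients and non-serious injection intolerance in up to 12. How many events would be lost cannot be derived from the documents; over the assumed range of 5% to 50% per patient, the chance of at least one minor biopsy event among the 4 runs from 18.5% to 93.8%.

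This rests on two assumptions: that staff apply the definition as worded, and that expectedness is judged by the risks named in F.1.c and F.2.b as well as in F.5. If staff follow the reporting plan instead, the events are counted but the definition is breached. Either way the text needs reconciling. The primary endpoint and the capture of serious and unexpected events are unaffected, so this is a change that should be made for the quality of the safety data; it does not put the study's main result in doubt.

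**What to change.** 1. In F.5, define an adverse event as any untoward sign, symptom or finding after the first study procedure, whether or not expected and whether or not serious. Record each with severity grade, seriousness and attribution.
2. Use one list of expected risks, the same in F.1.c, F.2.b and F.5, so that bruising, hematoma, pain and injection intolerance are classed in one way.
3. Do not keep the present definition as a separate trigger for prompt reporting. It turns on seriousness, while the existing 24-hour rule turns on severity and/or lack of anticipation. Two triggers would then run side by side. Reconcile the terms and state a single rule.
4. For the annual comparison, say which of the two serious-event figures applies to which set of events. Report expected non-serious events as counts, since the plan states no rate for them.

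The cost is one revised definition, one aligned list and a few more lines on the event form for 12 participants. No visit, procedure or sample size changes.
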